## Synopsis

design	Prospective cohort study (population-based surveillance and serial sero-survey)
study site & population	
Polana Caniço, peri-urban Maputo, Mozambique: a health- and demographic surveillance site (HDSS) covering a population of approximately 15,393, in the catchment area of the Polana Caniço General Hospital (PCGH).
 
All individuals residing in the 2108 HDSS households for at least 3 months (infants, children, adults, elderly) are included in bi-weekly surveillance rounds, regardless of age.
 
An age-stratified random sample of that population (800 per age stratum) will be selected for the repeated sero- and social mixing survey.
 
No exclusion criteria apply for participants able and willing to provide consent for participation in the study.

duration	December 2020-December 2021 (12 months)

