## 4. Participants, Population & Selection

### 4.1 Setting

Polana Caniço, peri-urban Maputo, Mozambique: a health- and demographic surveillance system (HDSS) covering a population of 15,393, in the catchment area of the Polana Caniço General Hospital (PCGH), one out of two COVID-19 referral facilities in Maputo.

The population in peri-urban Polana Caniço is relatively representative of the increasingly urban population in Southern Africa, having young and mobile inhabitants. Moreover, the population suffers increasingly from non-communicable diseases, and prevalence of HIV and active tuberculosis is presumed to be important. Research gaps on COVID-19 transmission dynamics include whether the reproduction number could be different in such different (eg. younger) population. Also, the potential association between (uncontrolled) HIV infection or (active) tuberculosis and COVID-19 infection and severe disease, needs to be elucidated.

The Polana Caniço-HDSS has been established since 2017. In total, as of time of writing, 2108 households (defined as residents of the same building, sharing a cooking area) have been enrolled in the HDSS. All members residing in the household for at least 3 months (infants, children, adults, elderly) are enrolled in the HDSS. Surveillance rounds are currently carried out six-monthly. Demographic and health indicators collected in each surveillance round include but are not limited to: fertility/birth rate, mortality/cause of death, migration, disease cases, trauma and violence, socioeconomic status, water and sanitation facilities, risk factors for the acquisition of chronic diseases, women's health and family planning, immunization, risk behaviours and cultural practices related to the transmission of STI (including HIV and syphilis). Testing for HIV and syphilis is planned to be added as part of the surveillance rounds, from October 2020 onwards. Data on births, deaths, internal and external migration, pregnancies and their outcomes, and any other relevant events from a demographic perspective, are continuously reported by community key informants and confirmed through home visits.

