## 7. Statistical Analyses

### 7.1 Methods

All estimated transmission or clinical outcome indicators will be adjusted for the design effect, related to the selection of HDSS enumeration areas (clusters) within the source populations. Intraclass correlation coefficients can be deducted from previous studies in the HDSS. The results of the sero-survey and social mixing survey will additionally be adjusted for age-stratified sampling.

We will calculate a incidence rate of COVID-19 disease throughout one year, adjusting for the sensitivity of SARS-CoV-2 RT-PCR on nasal swabs by delay between symptom onset and testing. Using the longitudinal sero-survey data, determining the proportion of asymptomatics, we will be able to adjust the clinical incidence rate to a SARS-CoV-2 infection incidence rate, and determine the SARS-CoV-2 infection annual attack rate and the infection fatality risk by age group.

We will undertake three risk factor analyses: of SARS-CoV-2 infection, of COVID-19 disease (symptomatic infection), and of COVID-19 hospitalisation and death (severe disease). Using negative binomial regression, we will investigate the association with socio-demographic factors, clinical characteristics such as underlying medical conditions, and uptake of preventive measures. We also investigate the association between SARS-CoV-2 infection (from the sero-survey) and recent exposure, contact and mobility patterns (from the social mixing questionnaire).

We will assume everyone will be susceptible initially and basic and effective reproductive numbers ( $R_0$  and  $R_e$ ) will be calculated by the rate of change of incidence over successive serial intervals (time between onset of infection of index and onset of infection of infected).

We will use established methods (Cauchemez et al 2004; te Beest et al 2013) to estimate generation time distribution, ratio of transmissibility between symptomatic and asymptomatic cases, duration of

the infectious period, and the basic reproduction number, from the transmission data collected in households.

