## 7.2 Sample size and power

Assuming a 40% annual attack rate, 50% symptomatic infections (cases), 2% overall case fatality risk, of which 90% are identified by the active population surveillance, 2790 COVID-19 cases and 56 deaths will be identified through the study period. The average incidence rate of the HDSS population would then be 1.50 cases per 100 person months with lower and upper 95% confidence interval limits 1.45 and 1.56. The overall case fatality risk would have as lower and upper 95% confidence interval limits at 1.53 and 2.58%.

To determine the infection attack rate from a simple random population sample of three age strata (comparable in size), with +/-3% confidence limits, 95% confidence interval, assuming the attack rate may reach 40% towards the end of the study period, samples from 800 individuals per age stratum per round will need to be collected.

Assuming the household secondary attack rate to be close to 17% (Fung et al, Clin Infect Dis, 2020) and a median household size of 7.3 (based on HDSS data), a 5% confidence limit and a design effect of 3, 642 household members will need to be enrolled, or 100 households. The WHO also recommended to include 100 households in household transmission investigations.

Assuming 20% vaccination coverage among the 2400 sero-survey participants, 5% of sero-conversion over 3 months and 10% of seroconversion over 6 months, a 95% two-sided confidence interval and an anticipated crude total vaccine effectiveness of 50%, there will be 66% power to observe this effect after 3 months and 97% power after 6 months.

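### Section 7.2 states the incidence interval (1.45–1.56) without the design effect that section 7.1 promises, and the vaccine-effectiveness power appears to omit it too

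*Combined protocol and SAP*

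**What the plan says.** Section 7.1 (Methods) opens with a general commitment: "All estimated transmission or clinical outcome indicators will be adjusted for the design effect". The sentence goes on to tie this to HDSS enumeration areas as the clusters, and the next says that ICCs are obtainable from previous HDSS studies. Sero-survey results are to be corrected for age stratification on top of this, so both corrections apply to them.

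Section 7.2 (Sample size and power) then gives planning figures in four separate paragraphs:

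- Incidence and case fatality: the starting values are an attack rate of 40% over the year, half of infections with symptoms, and a fatality risk of 2% among cases. The expected yield is given as "of which 90% are identified by the active population surveillance, 2790 COVID-19 cases and 56 deaths will be identified". The projected rate is "1.50 cases per 100 person months with lower and upper 95% confidence interval limits 1.45 and 1.56", and the case-fatality limits are 1.53% and 2.58%. No design effect is named.
- Infection attack rate from the sero-survey: 800 per age stratum. No design effect is named.
- Household secondary attack rate: "a 5% confidence limit and a design effect of 3, 642 household members will need to be enrolled".
- VE against seroconversion: with 20% coverage among 2,400 participants and 50% effectiveness, "there will be 66% power to observe this effect after 3 months and 97% power after 6 months". No design effect is named.

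Table 1 marks COVID-19 disease incidence in bold, that is, as a primary outcome measure.

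**The concern.** The precision in 7.2 should describe the analysis in 7.1. If 7.1 widens every interval for clustering while 7.2 computes as if people were independent, the study will report a less precise primary outcome than its plan states. The authors had the idea of a design effect in hand, because they used one for the household calculation.

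The VE powers matter because they are the only powers in the plan. The 3-month figure is already low at 66%. A reader who takes it at face value may read too much into a null 3-month result if the effective sample is smaller than 2,400.

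**Working it through.** **Inputs.** From 7.2: attack rate 40%, symptomatic share 50%, detection 90%, 2,790 cases and 56 deaths; for VE, 2,400 participants, 20% vaccinated (480 against 1,920), seroconversion 5% at 3 months and 10% at 6 months, effectiveness 50%, two-sided 95%. From 4.1: the HDSS is described as "covering a population of 15,393". Follow-up is 12 months.

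**Step 1: reproduce the incidence interval.** 2,790 / (0.4 × 0.5 × 0.9) = 15,500 people, so the plan used a rounded population (15,393 gives 2,771 cases and the same rate). Person-months = 15,500 × 12 = 186,000, and the rate = 2,790 / 186,000 = 1.50 per 100.

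- Poisson interval on the log scale: 1.50 × exp(±1.96/√2,790) = 1.445 to 1.557, printed as 1.45–1.56.
- Exact Poisson: also 1.445 to 1.557.

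The printed interval therefore has a design effect of 1.

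**Step 2: case fatality.** 56/2,790 = 2.01%. The mid-P exact binomial interval is 1.53% to 2.58%, as printed. This too treats cases as independent.

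**Step 3: the household calculation, for contrast.** 3 × 0.17 × 0.83 × 1.96² / 0.05² = 650, or 641.5 with a finite population correction, against 642 printed. The design effect is applied here.

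**Step 4: VE power without a design effect.** Power = Φ[(p0 − p1 − 1.96·SE0)/SE1], where SE0 uses the pooled proportion and SE1 the separate proportions.

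- 3 months, risk ratio 0.5: p0 = 0.05, p1 = 0.025, SE0 = 0.01058, SE1 = 0.00869. The argument is 0.491 and the power 68.8%.
- 6 months, risk ratio 0.5: p0 = 0.10, p1 = 0.05, SE0 = 0.01460, SE1 = 0.01208. The argument is 1.770 and the power 96.2%.
- Odds ratio 0.5, pooled: 65.9% and 93.6%.
- Odds ratio 0.5, unpooled: 79.4% and 97.1%.
- Exact power of Fisher's test, risk ratio 0.5: 67.7% and 95.6%.

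None of these variants gives both 66% and 97%. The nearest matches to the pair are independence formulas, but the method used is not identified.

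**Step 5: what a design effect would do.** The documents give no ICC, no number of enumeration areas and no area size, so the values below are assumptions. The standard error is multiplied by √d.

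| Design effect d | Incidence interval per 100 person-months | Half-width 1.96 × 1.50 × √(d/2,790) |
|---|---|---|
| 1.0 | 1.45–1.56 | 0.056 |
| 1.2 | 1.44–1.56 | 0.061 |
| 1.5 | 1.43–1.57 | 0.068 |
| 2.0 | 1.42–1.58 | 0.079 |

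| Design effect d | VE power at 3 months | VE power at 6 months |
|---|---|---|
| 1.0 | 69% | 96% |
| 1.19 | 60% | 92% |
| 1.37 | 53% | 88% |

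The VE rows use risk ratio 0.5 and the pooled test. The value 1.37 is an illustration, not an estimate. It takes the ICC that a design effect of 3 with 6.3 contacts would imply, (3 − 1)/(6.3 − 1) = 0.377, applies it to a sample of 2,400 out of 15,393, and supposes that whole households share vaccination status: 1 + 0.156 × 6.3 × 0.377 = 1.37. Half that excess gives 1.19. If vaccination is unrelated within households, the value is 1.0.

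**The case against.** Several counter-arguments carry weight.

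**The 3 belongs elsewhere.** A reader might put the household design effect of 3 on the incidence rate and conclude that the interval should be about 1.41–1.60. The documents do not support this. The 3 concerns secondary infection among contacts in households chosen because they contain a confirmed case. Incidence is measured in all consenting HDSS households, and 7.1 names enumeration areas, not households, as the clusters.

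**Overstated VE power is not shown.** A reader might also infer that 66% and 97% are definitely too high. That goes beyond the evidence. The sero-survey is a simple random sample of individuals within age strata, about 1.1 per household (2,400 over 2,108). For a contrast between people who differ within clusters, the inflation can be close to nothing. The formula behind the printed pair is also unknown: pooled risk-ratio power with a design effect of 1.06 gives 66% at 3 months, though 95% rather than 97% at 6 months.

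**The effect on incidence is small, and the analysis is protected.** At a design effect of 1.5 the limits move by 0.01 to 0.02, and 7.1 already promises the correction at analysis. VE is a secondary objective. This limits the seriousness of the point, but the stated precision still does not describe the planned analysis.

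**The whole HDSS is under surveillance.** One could argue that no clusters are sampled. But 7.1 makes the commitment regardless, and the primary objective refers to peri-urban Maputo.

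**Conclusion.** For the incidence rate the point is established. The printed interval is an independence interval, 7.1 commits to a clustered analysis, and any design effect above 1 makes the reported interval wider than the stated one. The case-fatality interval has the same omission.

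The amount is not established. Between design effects of 1.2 and 2 the half-width grows by 10% to 41% (√1.2 = 1.10, √2 = 1.41). That range is an assumption, not a bound: enumeration-area size is unknown, and with large areas even a small ICC could exceed it.

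For VE the conclusion is weaker. The powers appear to take no account of the 7.1 correction and may be optimistic, by an amount that depends on how strongly both seroconversion and vaccination cluster. Zero loss remains possible.

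This should be corrected because it concerns the stated precision of a primary outcome and is cheap to put right. It does not threaten the design.

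**What to change.** In 7.2:

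1. Take ICCs for comparable outcomes from the earlier HDSS studies mentioned in 7.1, and give them with the enumeration-area size.
2. State the design effect assumed for each calculation, at the cluster level for which 7.1 corrects. If household clustering is also intended, say so in 7.1 and give its value separately.
3. Restate the incidence interval, the case-fatality interval and the VE powers with those values, or over a short range if the ICC is uncertain. Name the test and the effect measure behind the VE power so that it can be reproduced.
4. Do not carry the household value of 3 over to these quantities.

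The cost is a few lines of recalculation. Enrolment, procedures and objectives stay as they are. The only downside is that the stated precision, and possibly the power, will look less favourable.

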Household contact investigation at 1 day after confirmation of the household index case and 28 days after index case symptom onset	First 100 households with $\geq 1$ confirmed case; median household size 7.3 $\Rightarrow 100*6= 600$ household contacts	
 
• Household secondary infection rate
 
• Risk factors for household infection
 
• Risk factors for household infection resulting in Covid19 disease
 
• Total vaccine effectiveness against COVID-19
 

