An **age-stratified random sample** of that population will be selected for the **repeated sero- and social mixing survey**. By age stratum (0-17 years; 18-50 years; >50 years) we randomly select 800 individuals (simple random sample per age stratum; 2400 in total) from the Polana Caniço HDSS population (regardless of infection or disease status or history), from whom during home visits dried blood spots will repeatedly be collected at 0, 3, 6 and 12 months, vaccination status against COVID-19 will be recorded, and who will be asked to respond to a social mixing questionnaire. A HDSS sampling frame of all individual participants in the HDSS with socio-demographic data and unique identifiers, is available, and will be used to select a simple random sample of individuals by age group.

When a member of a household with no prior widespread transmission (see exclusion criteria) tests SARS-CoV-2 positive, we will revisit the household twice for a household transmission investigation: as soon as possible after the result of the household index case (baseline), and once again one month after symptom onset of the household index case. An initial contact report form will be filled in as soon as possible, ideally within 24 hours, after laboratory confirmation of the primary case in the household. Respiratory and dried blood spot samples will be collected of everyone considered resident (as defined by the HDSS) in the household and who has been in contact with the SARS-CoV-2 positive individual, regardless of age and presence or absence of symptoms. Respiratory samples will be analysed by RT-PCR for SARS-CoV-2 to assess presence of virus and viral load. The dried blood spots for serology on the Luminex assay. Data will be collected on household exposures of contacts and vaccine receipt. Symptomatic household contacts will be tested whenever symptoms appear, as part of the population-based surveillance. This is planned for upto 100 household index cases.

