### 4.3 Inclusion and exclusion criteria

In order to be eligible, study participants **must meet the following criteria**:

- » Any individual enrolled in the Polana Caniço-HDSS: all members residing in the household for at least 3 months (infants, children, adults, elderly), regardless of age, underlying conditions, medical history, infection or disease status or history;
- » Able and willing to provide written informed consent: by the household head for the surveillance; by each selected participant for the sero-survey and household investigations.
- » For household investigations, over 50% of the eligible household members and index case should have provided consent for anyone in the household to enrol.

Excluded from the household investigations: members of households in which more than 3 household members (including the index case) are known to have tested positive for SARS-CoV-2 in the past 7 days.

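### The stated 800 per age stratum does not give ±3% at a 40% attack rate (the stated inputs need 1,025, or 855 with a finite population correction), and the 642 in section 7.2 does not match Table 1's 600 household contacts

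*Combined protocol and SAP*

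**What the plan says.** Section 7.2 bases the sero-survey on "three age strata (comparable in size), with +/-3% confidence limits, 95% confidence interval", with an attack rate that could be as high as 40% by the end of the study. It concludes that "samples from 800 individuals per age stratum per round will need to be collected". It does not say whether the ±3% applies to each stratum or to the whole population, and it mentions neither a design effect nor a finite population correction for this survey.

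Section 7.1 says that "All estimated transmission or clinical outcome indicators will be adjusted for the design effect", but gives no value. It also says the study will "determine the SARS-CoV-2 infection annual attack rate and the infection fatality risk by age group".

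For the household study, section 7.2 assumes a 17% secondary attack rate, a 5% confidence limit, a design effect of 3 and a median household size of 7.3. It concludes that "642 household members will need to be enrolled, or 100 households". Table 1 takes the same 100 households at 6 contacts each and arrives at 600 contacts. Section 4.2 sets the ceiling: "This is planned for upto 100 household index cases".

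**The concern.** A precision-based sample size should be recoverable from its stated inputs. The sero-survey figure is not. The natural reading, ±3% in each stratum, needs more than 800, and the other reading, ±3% overall, needs far fewer than 2,400. The annual attack rate is the bold primary outcome of this survey in Table 1, so a reader will want to know what precision was planned and for which estimate.

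The household calculation raises a smaller question. The secondary infection rate is a primary objective, and section 7.1 defines its conventional estimate among household contacts. Section 7.2 and Table 1 give different counts for the same 100 households.

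**Working it through.** **Inputs.** From section 7.2: p = 0.40, d = 0.03, 95% confidence (z = 1.96), simple random sampling, strata of similar size, 800 per stratum. From section 4.1: population 15,393. Equal strata are an assumption based on the wording about comparable size: 15,393 / 3 = 5,131.

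**Formulas.**
- Without correction: n = DEFF·z²·p(1−p) / d².
- With finite population correction: n = DEFF·N·p(1−p) / [(d²/z²)(N−1) + p(1−p)].
- Half-width: z·√(DEFF·p(1−p)/n), multiplied by √((N−n)/(N−1)) if corrected.

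**1. Can 800 per stratum be reproduced?** (DEFF = 1)
- No correction: 3.8415 × 0.24 / 0.0009 = 1,024.4, so 1,025 (28% above 800).
- Correction with N = 5,131: 1,231.44 / (1.2019 + 0.24) = 854.0, so 855 (7% above 800).
- Variants that also fail: correction with N = 15,393 gives 961; 90% confidence gives 722; p = 50% gives 1,068 (884 with correction); scaling 854 for the 10% refusal in section 5.2 gives 769 (× 0.9) or 949 (/ 0.9).

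**2. What 800 delivers at 40%.**
- No correction: 1.96 × √(0.24/800) = 3.39 points.
- Correction with N = 5,131: 3.39 × √(4,331/5,130) = 3.12 points.
- 800 meets ±3 points only up to an attack rate of about 25% without correction (3.8415 × 0.1875 / 0.0009 = 800.3), or about 33% with it.

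**3. The overall reading.** With 2,400 people in equal strata:
- No correction: 1.96 × √(0.24/2,400) = 1.96 points.
- Correction with N = 15,393: 1.96 × √(12,993/15,392) = 1.80 points.

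An overall ±3 points would need only 1,025 people in total (961 with correction), not 2,400.

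**4. Household study.** With p = 0.17, d = 0.05, DEFF = 3 and N = 15,393: 3 × 15,393 × 0.1411 / (10.017 + 0.1411) = 641.4, so 642. The plan's figure reproduces. Without the correction it would be 650.4.

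Is 642 a count of contacts or of all members? At 7.3 − 1 = 6.3 contacts per household, 642 / 6.3 = 102 households, close to the stated 100. At 7.3 members, 642 / 7.3 = 88, which is not. Contacts is the better reading.

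Expected contacts from 100 households are 600 in Table 1, or 630 at 6.3 each: 42 or 12 below 642. Half-widths at DEFF 3 without correction:
- 642: 1.96 × √(3 × 0.1411/642) = 5.03 points
- 630: 5.08 points
- 600: 5.21 points

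The planning formula with correction, solved for d, gives 5.05 at 630 and 5.17 at 600.

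**The case against.** **The gap is close to rounding.** Section 7.2 gives precision in whole percent, and both 3.12 and 3.39 round to 3. The 40% is a level that may be reached late in the study, so earlier rounds with lower attack rates would meet the target. This stands as to size. It does not make 800 the number that the stated inputs require.

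**The strata may not be equal.** A stratum of about 3,650 or fewer would meet ±3 points with 800. But three such strata would total at most 10,950, short of 15,393. At least one stratum must hold 5,131 or more, and there the half-width at 40% is at least 3.1 points.

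**The target may be the overall rate.** In section 7.1 the words about age group close a list and may attach only to the fatality risk, and Table 1 gives the attack rate no age qualifier. On that reading the survey is more precise than stated. This is fair, and it is why the plan should say which reading is meant; it still does not explain 800 per stratum.

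**A reader might infer a hidden design effect.** Dividing 2,400 by 960.5 gives 2.50, and 642 reproduces with the same formula, so one could suppose an overall target with a design effect of 2.5 and conclude that each age group is really planned at about ±5 points. The documents do not support this. No section states that value; it is obtained only by solving backwards. It sits badly with simple random sampling of individuals, and section 7.1 ties the design effect to selection of enumeration areas. Nor is it the only route to 800, since a 25% attack rate also gives it.

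**The household part is minor, and 642 is worded as members.** Both are true. Section 7.2 also supports the 100 households by a WHO recommendation.

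**Conclusion.** The concern holds as a limited arithmetic and reporting point. On the stated inputs, 800 per stratum gives about ±3.4 points at a 40% attack rate without a finite population correction, or about ±3.1 with it, against ±3 stated. The second figure assumes equal strata of 5,131, and both are before any design effect. On the overall reading, 2,400 gives about ±2.0 points (1.8 corrected), so the stated requirement does not follow there either.

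The household mismatch is real but small: about ±5.1 to 5.2 points at 630 to 600 contacts, against ±5 stated. It rests on reading 642 as contacts and on investigated households being of the stated size.

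Two stronger conclusions should not be drawn. The documents do not show that the sero-survey is materially too small. They also give no basis for a much wider household interval from non-participation: section 4.3 requires that "over 50% of the eligible household members and index case should have provided consent for anyone in the household to enrol", but that is an eligibility floor for each household, not an expected average, and no participation rate is given.

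**What to change.** In section 7.2:
- Say whether ±3% is per stratum or overall, and whether a finite population correction is used.
- Restate the per-stratum precision of 800 at a 40% attack rate as about ±3.1% (with correction, equal strata) or ±3.4% (without).
- State any design effect actually used for the sero-survey; if none was used, say so.
- Label 642 as household contacts, if that is what it is, and mention the correction on 15,393 behind it.

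In section 7.2 and Table 1 together, reconcile 642 with 600 (or 630 at 6.3 contacts per household) and restate the household precision as about ±5.1% to 5.2%.

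The cost is a text change in section 7.2 and Table 1. Enrolment, estimands and analyses stay as they are, and the stated per-stratum and household precision becomes slightly less favourable.
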